10.1.4 Pregnancy reporting

Pregnancies

All childbearing women will have a local serum β -hCG test (serum pregnancy test) performed at screening. From baseline onwards monthly local urine pregnancy tests will be performed as indicated in the Assessment schedule. A positive urine pregnancy test requires immediate interruption of study drug until serum β -hCG is performed and found to be negative. Additional pregnancy testing might be performed if requested by local requirements.

If a female trial participant becomes pregnant, the patient must be asked to read and sign pregnancy consent form to allow the Study Doctor ask about her pregnancy.

To ensure subject safety, each pregnancy occurring after signing the informed consent must be reported to Novartis within 24 hours of learning of its occurrence. The pregnancy should be followed up to determine outcome, including spontaneous or voluntary termination, details of the birth, and the presence or absence of any birth defects, congenital abnormalities, or maternal and/or newborn complications. The follow-up for pregnant participants should be done 1 month, 3 months (for a live birth only) and 12 months (for a live birth only) after estimated date of delivery.

Pregnancy should be recorded and reported by the investigator to the Novartis Chief Medical Office and Patient Safety (CMO&PS). Pregnancy follow-up should be recorded on the same form and should include an assessment of the possible relationship to the investigational treatment any pregnancy outcome. Any SAE experienced during pregnancy must be reported.

The study drug must be discontinued, though the subject may stay in the study, if she wishes to do so. All assessments that are considered as a risk during pregnancy must not be performed. The subject may continue all other protocol assessments.

10.1.5 Reporting of study treatment errors including misuse/abuse

Medication errors are unintentional errors in the prescribing, dispensing, administration or monitoring of a medicine while under the control of a healthcare professional, subject or consumer (EMA definition).

Misuse refers to situations where the medicinal product is intentionally and inappropriately used not in accordance with the protocol.

Abuse corresponds to the persistent or sporadic, intentional excessive use of a medicinal product, which is accompanied by harmful physical or psychological effects.

Study treatment errors and uses outside of what is foreseen in the protocol will be collected in the DAR (dose administration record) eCRF irrespective of whether or not associated with an AE/SAE and reported to Safety only if associated with an SAE. Misuse or abuse will be collected and reported in the safety database irrespective of it being associated with an AE/SAE within 24 hours of Investigator's awareness.

Table 10-1 Guidance for capturing the study treatment errors including misuse/abuse

Treatment error type	Document in Dose Administration (DAR) eCRF (Yes/No)	Document in AE eCRF	Complete SAE form
Unintentional study treatment error	Yes	Only if associated with an AE	Only if associated with an SAE
Misuse/abuse	Yes	Yes	Yes, even if not associated with a SAE

For more information on AE and SAE definition and reporting requirements, please see the, respective sections.

10.2 Additional Safety Monitoring

Not applicable.

11 Data Collection and Database management

11.1 Data collection

Designated investigator staff will enter the data required by the protocol into the Electronic Case Report Forms (eCRF). The eCRFs have been built using fully validated secure web-enabled software that conforms to 21 CFR Part 11 requirements, Investigator site staff will not be given access to the EDC system until they have been trained. Automatic validation programs check for data discrepancies in the eCRFs, allow modification and/or verification of the entered data by the investigator staff.

The investigator/designee is responsible for assuring that the data (recorded on CRFs) (entered into eCRF) is complete, accurate, and that entry and updates are performed in a timely manner. The Investigator must certify that the data entered are complete and accurate.

After final database lock, the investigator will receive electronic copies of the subject data for archiving at the investigational site.

All data should be recorded, handled and stored in a way that allows its accurate reporting, interpretation and verification.

11.2 Database management and quality control

Novartis personnel (or designated CRO) will review the data entered by investigational staff for completeness and accuracy. Electronic data queries stating the nature of the problem and requesting clarification will be created for discrepancies and missing values and sent to the investigational site via the EDC system. Designated investigator site staff are required to respond promptly to queries and to make any necessary changes to the data.

Concomitant treatments and prior medications entered into the database will be coded using the WHO Drug Reference List, which employs the Anatomical Therapeutic Chemical classification system. Medical history/current medical conditions and adverse events will be coded using the Medical dictionary for regulatory activities (MedDRA) terminology.

Randomization codes and data about all study treatment (s) dispensed to the subject and all dosage changes will be tracked using an Interactive Response Technology (IRT) system. The data will be sent electronically to Novartis/ at specific timelines.

Each occurrence of a code break via IRT will be reported to the clinical team and monitor. The code break functionality will remain available until study shut down or upon request of Novartis.

Once all the necessary actions have been completed and the database has been declared to be complete and accurate, it will be locked and the treatment codes will be unblinded and made available for data analysis. Any changes to the database after that time can only be made after written agreement by Novartis development management.

11.3 Site monitoring

Before study initiation, at a site initiation visit or at an investigator's meeting, a Novartis representative will review the protocol and data capture requirements with the investigators and their staff. During the study, Novartis employs several methods of ensuring protocol and GCP compliance and the quality/integrity of the sites' data. The field monitor will visit the site to check the completeness of subject records, the accuracy of data capture / data entry, the adherence to the protocol and to Good Clinical Practice, the progress of enrollment, and to ensure that study treatment is being stored, dispensed, and accounted for according to specifications. Key study personnel must be available to assist the field monitor during these visits. Continuous remote monitoring of each site's data may be performed by a centralized Novartis Clinical Research Associate (CRA) organization. Additionally, a central analytics organization may analyze data and identify risks and trends for site operational parameters and provide reports to Novartis clinical teams to assist with trial oversight.

The investigator must maintain source documents for each subject in the study, consisting of case and visit notes (hospital or clinic medical records) containing demographic and medical information, laboratory data, electrocardiograms, and the results of any other tests or assessments. All information on CRFs must be traceable to these source documents in the subject's file. The investigator must also keep the original informed consent form signed by the subject (a signed copy is given to the subject).

The investigator must give the monitor access to all relevant source documents to confirm their consistency with the data capture and/or data entry. Novartis monitoring standards require full verification for the presence of informed consent, adherence to the inclusion/exclusion criteria, documentation of SAEs, and of data that will be used for all primary variables. Additional checks of the consistency of the source data with the CRFs are performed according to the study-specific monitoring plan. No information in source documents about the identity of the subjects will be disclosed.

12 Data analysis and statistical methods

The analyses will be conducted on all subject data at the time when interim analyses occur and when the trial ends. The analyses will be performed on Cohort 1 and Cohort 2 separately unless otherwise specified. Any data analysis carried out independently by the investigator should be submitted to Novartis before publication or presentation.

12.1 Analysis sets

For all analysis sets, subjects will be analyzed according to the study treatment(s) received.

The safety analysis set will include all subjects who received any study drug.

The PK analysis set will include all subjects with at least one available valid (i.e., not flagged for exclusion) PK concentration measurement, who received any study drug and with no protocol deviations that impact on PK data.

The primary PD analysis set will include all subjects who received any study drug having no protocol deviations with relevant impact on PD data.

12.2 Subject demographics and other baseline characteristics

Demographic and baseline characteristics (e.g., SLEDAI-2K, BILAG-2004, Physician Global Assessment, Patient Global Assessment, CCI [REDACTED] and baseline steroid dose) will be listed by subject and summarized by treatment group. Categorical data will be presented as frequencies and percentages. For continuous data, mean, standard deviation, median, minimum and maximum will be presented.

Relevant medical histories and current medical conditions at baseline will be summarized separately by system organ class and preferred term, and by treatment group. They will also be listed by subject and treatment group.

12.3 Treatments

The safety set will be used for the analyses in this section. Categorical data will be summarized as frequencies and percentages. For continuous data, mean, standard deviation, median, minimum, and maximum will be presented.

The duration of exposure in weeks to study drug will be summarized by treatment group. The listing by subject and by treatment group will also be provided.

Concomitant medications and significant non-drug therapies prior to and after the start of the study treatment will be listed and summarized according to the Anatomical Therapeutic Chemical (ATC) classification system, by treatment group.

12.4 Analysis of the primary endpoint(s)

For either investigational drug, the primary analysis will compare active treatment with its matching placebo based on the PD analysis set within either cohort independently.

12.4.1 Definition of primary endpoint(s)

The primary endpoint is a composite of SRI-4 response at Week 29 with sustained reduction in oral corticosteroid from Week 17 through Week 29.

SRI-4 response is defined as below:

- having ≥ 4 points reduction from baseline in SLEDAI-2K score AND
- no new BILAG-2004 A and no more than one new BILAG-2004 B domain scores AND
- no worsening, i.e., < 10 mm increase from baseline if scaled 0-100 mm or 0.3-point increase from baseline if scaled 0 to 3 in the Physician's Global Assessment

Sustained reduction in oral corticosteroid is defined as below:

- ≤ 5 mg/day or \leq baseline dose, whichever is lower, at Week 17

AND

- No increase of that dose from Week 17 through Week 29 according to all of the following conditions.
 - total daily CS dose remains ≤ 30 mg/d prednisone or equivalent
 - any increased daily CS dose administered is ≤ 2 days within a 4-week treatment cycle from Week 17 to Week 29
 - daily CS dose is not increased within 2 weeks of Week 29 study visit

When all these criteria are met, the patient is a responder. Patients who receive rescue medication (see [Section 6.2.4](#)) will be considered as non-responder.

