Within the treatment cohort, blinded treatment with the investigational drug (VAY736 or CFZ533) or placebo will be administered on top of patients' stable standard of care therapy for SLE. Visits to assess safety and/or efficacy are scheduled at 4-week intervals. An additional safety visit is scheduled at Week 3 (within the placebo-controlled period) and Week 31 (within the open label period) where patients in Cohort 2 (CFZ533) will receive an additional treatment dose (see [Section 4.2.2](#)).

At the baseline visit Day 1, following patient eligibility confirmation and completion of all assessments, first dose of study drug/placebo will be administered. The last treatment in the blinded treatment period will be given at the Week 25 visit. The readout for the blinded treatment period will be performed at Week 29. Study drug will be administered every 4 weeks. Unless otherwise stated, all assessments must be completed BEFORE the next dose of study drug is administered.

Guided corticosteroid (CS) reduction

- Patients entering the study on a stable CS regimen are required to undergo a guided CS taper from baseline levels starting at Week 5 in order to achieve by Week 17:
 - a daily CS dose of ≤ 5 mg/day prednisone or equivalent,
 - or a CS dose that is less than the baseline dose, whichever is the lower dose.
- In addition, the patient should remain at the lowered CS dose achieved at Week 17 through to Week 29.
- Patients entering the study without background CS therapy should remain free of any CS regimen or increase in SoC DMARDs through to Week 29.
- Patients exceeding the rescue therapy allowances may continue in trial but will be labeled a non-responder for primary endpoint.
- During the open label phase, further reductions in patients' SoC CS and DMARDs may be made on an individual basis as deemed appropriate by the investigator. For details on the guided CS tapering please refer to [Section 6.2.2](#)

Open-label treatment phase

At the end of the Week 29 visit, after all assessments have been performed, the first -open label treatment will be administered. Patients in Cohort 1 will receive VAY736 and patients in Cohort 2 will receive CFZ533. Study drug will be administered every 4 weeks. The last treatment will be given at the Week 49 visit, and the End-of-Treatment (EoT) visit will be performed 4 weeks thereafter, at Week 53.

Follow-Up period

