6.2.2 Permitted concomitant therapy requiring action (guided CS tapering)

Corticosteroids. Patients on stable, maintenance dosing of oral corticosteroids (≤ 30 mg/day prednisone or equivalent) prior to randomization should continue this dosing level until Week 5. From Week 5 visit onwards, patients will undergo a guided CS dose reduction from baseline levels according to the following schedule:

- Achieve by Week 17 a prednisone dose or equivalent of ≤ 5 mg/day or less than CS dose at Baseline, whichever dose is lower.
- Any remaining corticosteroid dosing at Week 17 should subsequently be kept stable up to the Week 29 visit.
- Patients who are unable to reach these reduced CS dose level goals by week 17 or maintain these achieved CS dose levels through to Week 29 will be considered a non-responder for primary endpoint.
- Limited adjustments in CS dosing after Week 17 are provided (see [Section 6.2.4](#) Rescue medication and [Table 6-3](#) Prohibited medication).
- Further adjustments of corticosteroids and of other DMARD co-medications may take place during the open label period after Week 29 according to PI discretion.

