Tuberculosis test ⁷	X																		X	
Pregnancy test ⁵	X	X		X	X	X	X	X	X	X	X	X	X	X	X	X	X		X	
Hematology ⁷	X	X		X	X	X	X	X	X	X	X	X	X	X	X	X	X		X	
Clinical Chemistry ⁷	X	X		X	X	X	X	X	X	X	X	X	X	X	X	X	X		X	
CCI																				
Coagulation Panel ⁷	X	X ⁶					X ⁶				X ⁶								X ⁶	
Autoantibodies ⁷	X	X					X				X				X				X	
CCI																				
IMI blood sample ^{7, 16}		X			X					X										
IMI urine sample ^{7, 16}		X			X					X										
CCI																				
Steroid taper ¹¹					X	X	X	X												
PK Cohort 1 ¹²			X	X	X	X	X	X	X	X	X	X	X	X	X	X	X	X	X	
PK Cohort 2 ¹²			X ¹³	X	X ¹³	X	X ¹³	X	X	X	X ¹³	X	X ¹³	X	X ¹³	X	X ¹³		X	
Immunogenicity ^{12, 14}		X		X			X				X	X			X				X	
CCI																				

Epoch	Screening		Treatment																EoT
Visit Name	Screen	Base-line ²	Treatment – blinded period								Treatment – open label period								EoT
Visit Numbers ¹	1	20	110	120	130	140	150	160	170	180	190	200	210	220	230	240	250	260	299
Days	-28 ±2	-1 to 1	1	15 ±2	29 ±2	57 ±2	85 ±2	113 ±2	141 ±2	169 ±3	197 ±3	211 ±2	225 ±3	253 ±3	281 ±3	309 ±3	337 ±4	340 ±1	365 ±5
Weeks	-4	-1 to 1	1	3	5	9	13	17	21	25	29	31	33	37	41	45	49	49	53
Months	-1	-1 to 1	1	1	2	3	4	5	6	7	8	8	9	10	11	12	13	13	14

IRT	X	X ²³		X	X	X	X	X	X	X	X	X	X	X	X	X	X		X
Dose administration ²¹			X ²²	X ⁶	X	X	X	X	X	X	X ²²	X ⁶	X	X	X	X	X		

Adverse Events	As required																		
Concomitant Treatment	As required																		
Comments	As required																		

^X Assessment to be recorded in the clinical database, EoT – End of Treatment

¹ Visit structure given for internal programming purpose only

² Baseline visit may be combined with Visit 110 at Day 1

³ Body Weight, Height (screening only), Temperature, Blood Pressure, Pulse Rate

⁴ Only for Cohort 1 (VAY736); i.v. CS to be applied approximately 1 hour before first dose

⁵ Pregnancy test on Visit 1 (Screening) in serum, all other visits in urine, only females

CCI

⁷ Central Lab

CCI

¹¹ Corticosteroids should be tapered down to 5 mg/day or lower

¹² Samples are collected pre-dose unless otherwise stated

¹³ Cohort 2 (CFZ533): take one PK sample at pre-dose and another sample 90 min AFTER THE START of i.v. infusion

¹⁴ Cohort 1 (VAY736): serum Cohort 2 (CFZ533): plasma

CCI

¹⁶ Only selected sites

CCI

²¹ Dosing must be done after all assessments are completed, except for PK blood sampling in Cohort 2 (CFZ533) at visits V110, 130, 150, 190, 210, 230 and 250 where pre and post dose blood sampling is required

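### The Week 17 steroid criterion of the primary endpoint is worded in two incompatible ways, so a patient who enters on more than 0 and up to 5 mg/day and is still at that dose can be scored either way

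*Protocol*

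**What the plan says.** Two groups of sections state the Week 17 steroid condition.

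- **Endpoint definitions (protocol 12.4.1, SAP 7.1.1).** The Week 17 dose must be at or below 5 mg/day or at or below "baseline dose, whichever is lower, at Week 17". An unchanged low dose is enough.
- **Taper and design sections (protocol 6.2.2, protocol section 3, SAP 1.4).** Protocol 6.2.2 asks for 5 mg/day or less, or "less than CS dose at Baseline, whichever dose is lower". Section 3 asks for 5 mg/day or less, or "a CS dose that is less than the baseline dose, whichever is the lower dose", and SAP 1.4 repeats this. An unchanged low dose is not enough.

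Protocol 6.2.2 also attaches a scoring consequence. "Patients who are unable to reach these reduced CS dose level goals by week 17", or who do not hold the achieved dose "through to Week 29 will be considered a non-responder for primary endpoint".

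Patients on no corticosteroid at entry have their own rule in section 3: "Patients entering the study without background CS therapy should remain free of any CS regimen". Footnote 11 to Table 8-1 is a schedule note: "Corticosteroids should be tapered down to 5 mg/day or lower". The endpoint tables (protocol Table 2-1, SAP Table 1-1) describe the steroid dose as reduced.

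**The concern.** Both wordings decide responder status. Because 6.2.2 names the primary endpoint, its stricter goal cannot be set aside as advice to sites on tapering. The SAP does not settle the matter, since it carries one wording in 1.4 and the other in 7.1.1, and the public text states no order of precedence. The endpoint's label points to a reduction, while its formula accepts an unchanged dose for patients who start low.

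Sites would therefore work to one target while the analysis scores another. With 30 patients per arm, a few reclassified responders can change whether the efficacy criteria are met.

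**Working it through.** **Step 1: apply both wordings to the same patient.** Protocol 6.2.2 covers stable oral doses up to 30 mg/day, and the visible text gives no lower limit. The Week 17 condition becomes:

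| Entry dose (mg/day) | 12.4.1 and SAP 7.1.1 | 6.2.2, section 3 and SAP 1.4 | Still at entry dose at Week 17 |
|---|---|---|---|
| 0 | separate CS-free rule | separate CS-free rule | no conflict |
| 2.5 | at most 2.5 | below 2.5 | passes the first, fails the second |
| 5 | at most 5 | below 5 | passes the first, fails the second |
| 7.5, 10 or 30 | at most 5 | at most 5 | fails both |

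The conflict is confined to entry doses above 0 and up to 5 mg/day with no change by Week 17. A patient in that range who comes down at all passes both wordings, and one who goes up fails both.

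**Step 2: the plan's own figure.** Protocol 12.8.1 gives an 84% chance of meeting both efficacy criteria with 30 per arm, 17% on placebo and 42% on active (17 + 25), and around 10% if there is no difference. No numerical prior appears in the public text. Exact enumeration of two Binomial(30) arms with independent uniform priors and no covariates gives 81.2%, and 6.0% under no difference. A placebo prior worth 5 patients gives 84.4%. The 84% can be neither confirmed nor called wrong, and the point does not depend on it. The 81.2% is the reference below.

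**Step 3: how few responders decide.** Under the same uniform priors, the two criteria are P(difference > 0) > 0.90 and P(difference > 15 points) > 0.50.

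- 10 vs 5 responders: 0.93 and 0.525, so both are met.
- 9 vs 5 responders: 0.88 and 0.41, so neither is met.

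With up to 10 placebo responders, the active arm needs a surplus of 5.

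**Step 4: illustration of size.** Let s be the share of patients entering on more than 0 and up to 5 mg/day, and u the share of would-be responders among them who are still at entry dose at Week 17. Assume that s and u are the same in both arms and that these patients respond at the overall rate. Take 42% vs 17% as the rates under the 12.4.1 wording. Under the stricter wording each rate is multiplied by (1 − s·u).

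| s | u | 1 − s·u | Active vs placebo | Difference (points) | Chance of meeting both criteria |
|---|---|---|---|---|---|
| – | – | 1 | 42.0% vs 17.0% | 25.0 | 81.2% |
| 15% | half | 0.925 | 38.9% vs 15.7% | 23.1 | 76.9% |
| 15% | all | 0.85 | 35.7% vs 14.5% | 21.3 | 71.9% |
| 30% | half | 0.85 | 35.7% vs 14.5% | 21.3 | 71.9% |
| 30% | all | 0.70 | 29.4% vs 11.9% | 17.5 | 59.7% |

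The values of s and u are assumptions; the documents give neither.

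**Step 5: unequal arms.** With s = 20%, let u be 30% in one arm and 70% in the other. The chance is 81.5% if the placebo arm has more unchanged patients and 68.1% if the active arm does.

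**The case against.** The strongest reply is that the two formal definitions, protocol 12.4.1 and SAP 7.1.1, agree with each other, so the programmed analysis probably follows them. That is likely, and it narrows the problem. It does not remove it, because 6.2.2 still assigns the opposite status to the same patient in the protocol's own words. It is also fair that the study is described as non-confirmatory, that the criteria only guide decisions, and that SAP 7.1.2 already reports SRI-4, successful tapering and the composite separately. The supportive-analysis sections are blank in the public text and may hold a relevant analysis.

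Several stronger readings are tempting but not supported:

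- *Everyone entering on 5 mg/day or less is affected.* Patients on no corticosteroid have a separate rule, and those who taper at all satisfy both wordings.
- *Footnote 11 is a third scoring rule.* It assigns no responder status. It only needs aligning.
- *The rule could be picked after seeing the data.* Nothing shows this. SAP 1.1 places derived-variable specifications in a separate document that is not public.
- *Responders lost in one arm can be set directly against the surplus of 5.* Both arms would be reclassified, so part of the change cancels. In the illustration the difference falls by 1.9 to 7.5 points.
- *The wording biases the comparison in a known direction.* The rule applies to both blinded arms, and step 5 shows that the effect depends on which arm has more unchanged patients.

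**Conclusion.** The point stands. The documents contain two incompatible Week 17 rules, each tied to primary-endpoint status, and the SAP repeats both. Those affected entered on more than 0 and up to 5 mg/day, are still at that dose at Week 17, and meet every other component.

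How many there are is unknown. No baseline steroid distribution is given, and parts of inclusion criterion 6 and of the steroid conditions in Table 6-2 are redacted. The fall from about 81% to about 60–77% is an illustration. It rests on the assumed 15–30% share, half to all of the would-be responders among them unchanged, equal shares in both arms, uniform priors, no ENA or SLEDAI-2K terms, and the plan's 42% vs 17%. No view is taken here on which dose rule is right.

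**What to change.** 1. Reconcile protocol section 3, 6.2.2 and 12.4.1 and SAP 1.4 and 7.1.1 into one Week 17 criterion, and align Table 8-1 footnote 11 with it. SAP 1.4 must be included, or the conflict stays inside the SAP. The dose target is for the sponsor to decide.
2. State which rule the analysis applied and when it was fixed. Reconciling before any unblinding no longer looks possible, because SAP section 5 says that an earlier interim report gave the final CFZ533 results. A dated record is the available substitute.
3. Report the primary analysis under the other wording as a sensitivity analysis, with the number of patients reclassified in each arm.

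The cost is a wording change, one derived flag and one repeat of the model. No new data are needed: protocol 6.2.4 has concomitant medications and their dose changes recorded in the eCRF, and 12.2 already summarises baseline steroid dose.
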